**5.2 Treatment arms**

This is an open-label, single arm study; all of the patients will be assigned to 1-step titration treatment.

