2.5.2 Statistical hypothesis, model, and method of analysis

The change from baseline in MMSE total score will be analyzed using a mixed model repeated measures (MMRM) model. The model will contain visit as a fixed effect, baseline MMSE score as a covariate and subject as a random effect. An unstructured covariance matrix should be used. The estimated mean change at Week 24 along with a two-sided 95% confidence interval and p-value will be tabulated and presented graphically. P-values will be used in descriptive manner.

Further, the MMSE total score and change from baseline will be summarized using standard descriptive statistics by visits.

In addition, the primary endpoint will be summarized and analyzed by subgroups specified in [Section 2.2.1.1](#).

The MMRM model of subgroup analysis will contain visit, subgroup (categories) and visit*subgroup as fixed effects, baseline MMSE score as a covariate and subject as a random effect. An unstructured covariance matrix should be used. The estimated mean change at Week 24 along with a two-sided 95% confidence interval and p-value will be presented. P-values will be used in descriptive manner. Figures will only be provided for selected subgroup analysis as specified in [Section 2.2.1.1](#).

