2.13 Interim analysis

Not applicable.

3 Sample size calculation

The sample size is determined as precision-based for the change from baseline in MMSE score at week 24. Ninety-seven patients will ensure that the half-width of 95% confidence interval for the change from baseline in MMSE score at week 24 would be 0.6, assuming SD=3.0 which is estimated from 1301, 1303 and 1403 studies. Assuming drop-outs, a total of 120 patients will be enrolled to achieve at least 97 evaluable patients.

4 Change to protocol specified analyses

The following are considered for the analysis which was not planned during the time of protocol development:

1. Rate of responses for change from baseline in MMSE total score has been provided based on Full Analysis Set, Per Protocol Set and subjects with 3-step titration.
A responder is defined as those patients whose MMSE total score has remained unchanged from baseline till Week 24 or, patients whose MMSE total score has improved at Week 24 compared to baseline.
2. For Neuropsychiatric Inventory (NPI), the value 0 is considered wherever N/A or Absent has been marked in the eCRF page.
3. Visit Window for discontinuations: The study does not have a pre-defined visit windows for the entire study period. However, correct visit re-mapping for the discontinued patients was performed for summarizing and listing the efficacy and safety variables by visits. The last records of the discontinued patients are re-mapped to the actual visit when they discontinued rather than the Visit 8/discontinuation as per the assessment schedule of the protocol. Re-mapping was done for the discontinued patients to the nearest planned visit as per their actual discontinuation/ assessment date for each variable.

The following efficacy assessments: MMSE, NPI-10, QOL-AD, J-CGIC and Modified Crichton Scale were re-mapped for the considered discontinued patients as described above.

Under safety assessment, Vitals were considered for re-mapping for the discontinuation patients as described above. For other safety assessments, this re-mapping had no impact.

5 Appendix

This appendix gives details about statistical methods in addition to the report text. All analyses will be performed by using SAS version 9.4.

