5.3.1 Mixed Model Repeated Measures (MMRM) analysis

The change from baseline in MMSE total score will be analyzed using a mixed model repeated measures (MMRM) model. The model will contain visit as a fixed effect, baseline MMSE score as a covariate and subject as a random effect. An unstructured covariance matrix should be used.

```
proc mixed data = xxx ;
  class visit subjid;
  model chg = visit base /noint ddfm = KR alpha = 0.05;
  repeated visit /type = UN subject = subjid ;
  lsmeans visit /cl;
run;
```

where,

chg: change from baseline in MMSE total score

visit: study visits as per protocol assessment schedule,

base: baseline MMSE score

subjid: subject identifier.

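### If MMSE change is correlated with baseline, the primary Week 24 confidence interval is too narrow for the population mean change, because it treats the observed mean baseline as fixed

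*SAP*

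**What the plan says.** The trial has one arm: "This is an open-label, single arm study; all of the patients will be assigned to 1-step titration treatment" (Protocol Section 5.2). The primary model is a repeated-measures model for change in MMSE at Week 8 and Week 24, with "baseline MMSE score as a covariate and subject as a random effect" (SAP Section 2.5.2, matching Protocol Section 9.4.2). The code in SAP Section 5.3.1 is "model chg = visit base /noint ddfm = KR alpha = 0.05", with an unstructured covariance, and the results come from "lsmeans visit /cl". Baseline has one slope common to both visits.

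On reporting, the SAP states: "The estimated mean change at Week 24 along with a two-sided 95% confidence interval and p-value will be tabulated and presented graphically". It adds: "P-values will be used in descriptive manner".

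The sample size (SAP Section 3, Protocol Section 9.8) rests on the precision of this quantity: 97 evaluable patients, so that the "half-width of 95% confidence interval for the change from baseline in MMSE score at week 24 would be 0.6, assuming SD=3.0". Enrolment is 120.

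SAP Section 2.5.4 also plans one-sample t intervals for the same endpoint without a covariate, in completers and with LOCF. Neither document says that the primary interval is conditional on the observed baseline mean.

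**The concern.** With one arm, the Week 24 LS mean is itself the result. With complete data it equals the raw mean change, because the covariate is evaluated at its own sample mean. The covariate leaves the estimate where it was but takes the variance it explains out of the standard error. That variance has not gone away for the population mean change, since another sample would have another mean baseline. In a randomised comparison the same term would drop out of the difference between arms. Kenward-Roger does not restore it: that correction deals with estimating the covariance parameters, not with sampling of a covariate mean.

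At stake are the error bars of the quantity on which the trial is sized. If r is not zero, the reported interval covers the population mean change less often than 95%. It may also come out narrower than the planned 0.6 and be read as extra precision.

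**Working it through.** **Inputs.** SD of change 3.0, half-width 0.6, 97 evaluable and 120 enrolled (SAP Section 3); two-sided 95% (SAP Section 2.5.2); baseline MMSE 10 to 23 (Protocol Section 4.1). Assumed, because the documents do not give it: r, the correlation of Week 24 change with baseline. Only its size matters, not its sign.

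**1. The plan's own figure.** n = (1.96 × 3.0 / 0.6)² = 96.04, rounded up to 97. This reproduces. At n = 97 the half-width is 1.96 × 3.0 / sqrt(97) = 0.597, or 0.605 with the t quantile on 96 df. The SD used is the marginal SD of change, not a baseline-adjusted one.

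**2. The two standard errors, complete data.**
- For the population mean change: SD / sqrt(n).
- For the LS mean with mean baseline held fixed: SD × sqrt(1 - r²) / sqrt(n).
- Omitted variance: slope² × s_base² / n, where s_base is the SD of baseline MMSE. The ratio of widths is sqrt(1 - r²).

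Coverage of the nominal 95% interval for the population mean change is 2Φ(1.96 × sqrt(1 - r²)) - 1.

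**3. Results at n = 97, SD 3.0.** The last two columns use the normal quantile.

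| \|r\| | sqrt(1 - r²) | Half-width | Coverage |
|---|---|---|---|
| 0 | 1.000 | 0.597 | 95.0% |
| 0.1 | 0.995 | 0.594 | 94.9% |
| 0.2 | 0.980 | 0.585 | 94.5% |
| 0.3 | 0.954 | 0.570 | 93.9% |
| 0.4 | 0.917 | 0.547 | 92.8% |
| 0.45 | 0.893 | 0.533 | 92.0% |
| 0.5 | 0.866 | 0.517 | 91.0% |

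With the t quantile the half-widths are about 1% larger: 0.605 × 0.980 = 0.59 at 0.2, 0.605 × 0.954 = 0.58 at 0.3 and 0.605 × 0.893 = 0.54 at 0.45.

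**4. Check by simulation, complete data, one visit** (n = 97, 40,000 runs). At r² of 0, 0.05, 0.10 and 0.20, coverage was 95.0%, 94.4%, 93.5% and 92.1%, with mean half-widths 0.603, 0.588, 0.572 and 0.540. The t interval had 0.603.

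**5. Check closer to the planned model** (Week 8 and Week 24, common slope, 120 patients, 19% missing at Week 24, from 1 - 97/120). Coverage was 94.9%, 94.2% and 92.2% at |r| of 0.2, 0.3 and 0.45. An estimator equivalent to treating baseline as a response stayed at about 95%. A separate approximate run (5,000 trials, Monte Carlo error about 0.35 points) gave 94.3%, 93.8% and 93.0% at 0.2, 0.3 and 0.447.

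**6. Effect of the common slope.** If the fitted slope b differs from the true Week 24 slope β, the omitted variance is s_base² × b(2β - b) / n, which is largest at b = β. With no correlation at Week 8 and r = -0.3 at Week 24, a run of 1,200 trials gave a ratio of model to empirical standard error of 0.96 and coverage of 94.6% (Monte Carlo error about 0.6 points).

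**The case against.** Much of the case for leaving the plan alone stands.

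- **The shortfall is conditional.** A reader might infer that the planned interval simply is too narrow. The documents do not support that: they give no correlation, and at r = 0 nothing is lost.
- **The upper end is demanding.** Assume a baseline SD of 3.5 to 4.0 (a uniform spread over 10 to 23 gives 4.0). Then |r| = 0.45 needs a slope of 0.45 × 3.0 / 4.0 = 0.34 to 0.45 × 3.0 / 3.5 = 0.39. Expected change would differ by 4.4 to 5.0 points between baselines of 10 and 23. At |r| = 0.3 the difference would be 2.9 to 3.3 points, and the half-width loss is 0.597 - 0.570 = 0.027 points.
- **No decision turns on it.** P-values are descriptive, there is no success threshold, and Protocol Section 3.2 says that the study does not aim to show superiority or non-inferiority.
- **This is not the trial's only quantitative aim**, as a reader might infer from the sample size section. Protocol Section 9.6.3 and SAP Section 2.9.1.3 also ask, with a 95% interval, whether more than half of caregivers prefer the patch.
- **Covariate-free t intervals are already planned.** They do not have this defect, but they rest on completers or LOCF and so do not replace the MAR-based primary interval.
- **The interval is valid for the mean change at the observed mean baseline.** True, and saying so would be the least that is needed. But the SAP states no such target, and its sample size uses the marginal SD. A conditional interval would still not answer the question for which the trial was sized.

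**Conclusion.** The point holds in conditional form and is minor. For the code as written, the Week 24 interval is too short for the population mean change by about sqrt(1 - r²): nothing at r = 0, under 5% of the width for |r| up to 0.3, and about 11% (coverage about 92%) at 0.45. These figures rest on n = 97, SD 3.0, an assumed r and a common slope close to the Week 24 slope. Where the Week 8 and Week 24 slopes differ, the loss is smaller.

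The point estimate with complete data is not in question, and no test result is at risk. What should not happen is that a covariate-shortened interval is compared with the planned 0.6 and taken as added precision about the population mean change. The same applies to the subgroup LS means in SAP Section 5.3.2.

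**What to change.** Make the primary interval marginal over baseline, in one of two ways:

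1. Fit an unstructured repeated-measures model with baseline, Week 8 and Week 24 MMSE as three responses. Estimate the Week 24 minus baseline and Week 8 minus baseline contrasts with their intervals. Missing data are still handled under MAR.
2. Keep the planned model and its estimate, and obtain the interval by resampling patients, recomputing the mean baseline each time. Alternatively, add slope² × s_base² / n to the LS-mean variance. The added term is exact only when the common slope matches the Week 24 slope, so the bootstrap is safer if the slopes may differ.

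Record the choice in SAP Section 4 and apply it to the subgroup LS means.

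**Cost.** A few lines of SAS, no new data, and a slightly wider interval. With missing data, option 1 can also move the point estimate slightly, because it allows a separate baseline slope at each visit. It replaces the model named in Protocol Section 9.4.2, so the sponsor should check whether Protocol Section 11.1 calls for an amendment. Option 2 leaves that model in place.

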5.3.2 MMRM model of subgroup analysis

The MMRM model of subgroup analysis will contain visit, subgroup (categories) and visit*subgroup as fixed effects, baseline MMSE score as a covariate and subject as a random effect. An unstructured covariance matrix should be used.

```
proc mixed data = xxx ;
  class visit subgrcat subjid;
  model chg = visit subgrcat visit*subgrcat base / noint ddfm = KR alpha = 0.05;
  repeated visit /type = UN subject = subjid ;
  lsmeans visit*subgrcat /cl;
run;
```

where

chg: change from baseline in MMSE total score,

visit: study visits as per protocol assessment schedule,

subgrcat: subgroup categories,

visit*subgrcat: interaction effect of visit and subgrcat,

base: baseline MMSE score,

subjid: subject identifier.

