2.2.1 Subgroup of interest

2.2.1.1 Subgroup analyses for efficacy endpoints

The following subgroup analyses will be performed for the change from baseline in the total MMSE score at each post-baseline visit (i.e., Week 8 and Week 24):

- age (\leq 60 years, $>$ 60 years)*
- weight (\leq median, $>$ median, in kg, to be determined from the data)
- MMSE at baseline (10-14, 15-23 and further 15-23 into 15-19 and 20-23)*
- treatment regimen (e.g., overall, 1-step and 3-step titration)
- reason for switching to 3-step titration (as captured in the DAR page of CRF, e.g., adverse events, lab or test abnormality, lack of efficacy)
- Overall compliance to study medication (<75% and 75-100%)
- Patient profile analysis 1a: Use of skin moisturizer at baseline (yes/no)*
 - ◆ Total
 - ◆ Compliance to study medication (<75% and 75-100%)

Note: skin moisturizer will be identified using the data captured in the prior and concomitant medication CRF page and confirmed by the clinical team.

- Patient profile analysis 1b: Use of skin management at least one time during study period (yes/no)*
 - ◆ Total
 - ◆ Compliance to study medication (<75% and 75-100%)

Note: skin management will be identified using the data captured in the prior and concomitant medication CRF page and confirmed by the clinical team.

- Patients satisfying protocol inclusion criteria 9-1 only, 9-2 only and both, respectively captured in the CRF page, are specified below:*

- ◆ Inclusion criteria 9-1: Patients who are not responding to the previous treatment can be defined if the patients meet at least one of these conditions at baseline:
 - Patients who declined \geq 2 points of MMSE despite of treatment of other oral ChE inhibitors within initial 3-month and continued to show insufficient treatment effect until at baseline.
 - During 6 months prior to screening visit, Patients who declined \geq 2 points of MMSE with other oral ChE inhibitors and continued to show insufficient treatment effect until at baseline.
 - Patients who show marked worsening of BPSD, or ADL (can be defined by 1 state progression of FAST) judged by a physician despite

of treatment of other oral ChE inhibitors in initial 3-month or last 6-month with other oral ChE inhibitors

- ◆ Inclusion criteria 9-2: Patients having difficulties being treated orally with ChEIs (donepezil or galantamine) by physician's judgement. Difficulties are defined if the patients meet at least one of these conditions at baseline:*

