- Inadequate compliance with the ChE inhibitors at screening and baseline
- Inadequate treatment (efficacious dose was not reached or inadequate compliance) with the ChE inhibitors because of AEs except gastrointestinal (GI) symptoms (nausea and vomiting) at screening and baseline
- Patients with swallowing difficulties at screening and baseline

Further, a subgroup analysis will be presented for patients satisfying inclusion criteria

- 9-1 only, 9-2 only and both 9-1 and 9-2
- 9-1-1 only, 9-1-2 only, 9-1-3 only, and 9-1-1 and 9-1-3, and 9-1-2 and 9-1-3
- (9-1-1 or 9-1-2) versus (9-1-2 and 9-1-3) versus 9-1-3 only
- 9-1 versus 9-2
- (9-1 only) versus (9-1 and 9-2) or (9-2 only)
- (9-2 only) versus (9-1 and 9-2) or (9-1 only)

- Patients with concomitant use of memantine (yes/no)
- Patients satisfying treatment retention criteria as in Section 2.9.1 (yes/no)

Note: * items will also be illustrated using figures for the CSR.

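### The subgroup MMRM evaluates baseline-MMSE strata at the overall mean baseline, so an outer stratum's reported mean change refers to a baseline outside that stratum

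*SAP*

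**What the plan says.** SAP 2.2.1.1 lists the subgroups for MMSE change, among them "MMSE at baseline (10-14, 15-23 and further 15-23 into 15-19 and 20-23". This subgroup is starred, and starred "items will also be illustrated using figures for the CSR".

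SAP 2.5.2 states that "the primary endpoint will be summarized and analyzed by subgroups specified in" that section, and gives one model for all of them: "The MMRM model of subgroup analysis will contain visit, subgroup (categories) and visit*subgroup as fixed effects, baseline MMSE score as a covariate". The result is described as the estimated mean change at Week 24, with a 95% confidence interval and a descriptive p-value.

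SAP 5.3.2 codes this as "model chg = visit subgrcat visit*subgrcat base / noint ddfm = KR alpha = 0.05", followed by "lsmeans visit*subgrcat /cl". Baseline MMSE is not in the CLASS statement, so it is continuous with one common slope. There is no AT option, no separate fit by stratum and no exception for strata of baseline MMSE.

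SAP 2.2.1.1 also lists comparisons by inclusion criterion 9. They include 9-1 against 9-2, "9-1-1 or 9-1-2) versus (9-1-2 and 9-1-3) versus 9-1-3 only" and "9-1-1 only, 9-1-2 only, 9-1-3 only, and 9-1-1 and 9-1-3, and 9-1-2 and 9-1-3".

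**The concern.** Adjusting subgroup means to a common baseline is sensible when the subgroup is age, weight or memantine use. It is not when the subgroup is a band of the covariate. The 10-14 band is then reported as the change its patients would have at the overall average baseline, a value outside the band. That is a valid estimate of an extrapolated quantity. It is not the band's mean change, which is how SAP 2.5.2 describes it.

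Three things are at stake:

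- The interval for an outer band is wider than it need be.
- If change depends on baseline, the model removes the very gradient this subgroup is meant to show.
- The plotted values would then disagree with the descriptive band means that SAP 2.5.2 plans beside them.

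The overlapping criterion-9 groups are a second, smaller problem: a patient cannot sit in two levels of the single factor in SAP 5.3.2.

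**Working it through.** **The plan's own figure.** SAP section 3 assumes SD 3.0 and a half-width of 0.6: n = (1.96 × 3.0 / 0.6)² = 96.04, rounded up to 97. At n = 97 the half-width is 1.96 × 3.0 / √97 = 0.597. The figure reproduces and is not in dispute.

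**What follows from the text alone.** Eligible baselines run from 10 to 23 (Protocol 4.1, criterion 7). The overall mean is one number, so it lies in at most one of 10-14, 15-19 and 20-23. At least one outer band is therefore always evaluated outside its range, and both are for any mean above 14 and below 20.

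**Location.** With complete data and common slope b, the LS mean for band s is the band's observed mean change plus b × d, where d = overall mean baseline − band mean baseline.

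**Precision.** Take the coded two-visit model with complete data, variance σ² = 9 at both visits and correlation ρ between the Week 8 and Week 24 changes. The Week 24 variance for band s is

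σ²/n_s at the band's own mean, and σ²/n_s + d² × σ²(1+ρ) / (2 × SSW) at the overall mean,

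where SSW is the within-band sum of squares of baseline MMSE.

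**Assumed inputs.** The documents give neither the baseline distribution nor ρ. For the main case I take a normal distribution with mean 17 and SD 3.8, truncated to the integers 10-23, with expected counts for n = 97 and ρ = 0.5. The overall mean is 16.86 and SSW is 161.7. The slope-variance term is 9 × 1.5 / (2 × 161.7) = 0.0417.

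- 10-14: n = 24, mean 12.63, d = 4.23. Own mean: √(9/24) = 0.61. Overall mean: √(0.375 + 17.9 × 0.0417) = 1.06. Ratio 1.73. Half-widths 1.96 × SE: 1.20 and 2.08.
- 20-23: n = 22, mean 21.13, d = −4.28. Own mean: √(9/22) = 0.64. Overall mean: √(0.409 + 18.3 × 0.0417) = 1.08. Ratio 1.69. Half-widths: 1.25 and 2.12.
- 15-19: d = −0.14, ratio 1.00.

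**Range of SE ratios, ρ from 0.3 to 0.7**

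| Assumed baseline | Outer bands, three-level split |
|---|---|
| Normal, mean 17, SD 3.8 | 1.62-1.80 |
| Flat on 10-23 | 1.90-2.11 |
| Normal, mean 15 or 19, SD 3.8 | 1.52-1.74 |
| Normal, mean 17, SD 3.0 | 1.50-1.65 |
| Normal, mean 20, SD 3 | 1.28-1.50 |

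The middle band is unaffected only when the overall mean is near its centre. Its ratio is 1.14-1.18 for mean 15 (SD 3.8) and 1.28-1.36 for mean 20 (SD 3). In the two-level split, 10-14 has ratios of 1.09-1.49 over all these baselines.

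**Size of the shift.** The slope is not in the documents. A slope of 0 gives no shift. For the main case, assumed slopes of −0.1 to −0.3 per point give 4.23 × 0.1 = 0.42 to 4.23 × 0.3 = 1.27 points in 10-14, and about the same in 20-23.

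**Simulation of the coded model.** Assumptions: flat baseline, slope −0.2, N = 120, complete data, 400 runs. Week 24 results:

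| Band | As coded (SE) | At own mean (SE) | Observed mean |
|---|---|---|---|
| 10-14 | −0.55 (0.84) | +0.40 (0.45) | +0.40 |
| 15-19 | −0.47 (0.46) | −0.56 (0.45) | −0.56 |
| 20-23 | −0.46 (0.92) | −1.50 (0.50) | −1.50 |

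A gradient of 0.40 − (−1.50) = 1.90 points would be plotted as almost flat.

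**Overlapping groups.** Protocol 4.1 admits patients who meet 9-1, 9-2 or both, so 9-1 against 9-2 is not disjoint. In the three-way comparison, a patient with 9-1-2 and 9-1-3 is in the first two groups. In the last list, a patient with all three conditions is in both paired groups.

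**The case against.** The strongest case against has four parts.

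- **Nested reading.** The wording of the strata can mean a two-level model followed by a split within 15-23, rather than one three-level factor. On that reading the effect is smaller: over the same baselines and correlations, the ratio is 1.33-1.55 for 20-23 and 1.09-1.49 for 10-14, and the distance for 20-23 in the main case falls from 4.3 to 2.9 points. This stands as to size. It does not remove the problem, because each of the two models still has a band evaluated outside its range.
- **Slope.** The shift in the point estimate rests on slopes the documents do not give. This stands: the shift is a scenario. The wider interval does not depend on the slope.
- **Consequences.** Descriptive subgroup means are also planned, the covariate is disclosed, p-values are descriptive and the primary analysis is untouched. This stands and limits the importance. But the descriptive means do not correct the figure, and they may contradict it without explanation.
- **Overlap.** The SAP does not say that every listed comparison is one factor; separate yes/no models would satisfy the list, and a disjoint split of 9-1 only, 9-2 only and both is already there. Only the three-way comparison overlaps on its face; the other two overlap only if patients meet both criteria or all three conditions. That is fair, but the only subgroup code given uses a single factor, so the SAP should state the choice.

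**Conclusion.** The concern holds. As coded, at least one outer band of baseline MMSE is reported at a baseline outside its range, whatever the data. For a three-level split with 97 patients and SD 3.0, the standard error of an outer band is 1.28 to 2.11 times that at its own mean across the assumed baselines, and about 1.6 to 1.8 times in the main case. The shift in the estimate is zero if change is unrelated to baseline, and 0.4 to 1.3 points in the main case for assumed slopes of −0.1 to −0.3. Baseline distribution, visit correlation and slope are all assumptions, and the calculation ignores missing data.

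The scope is one exploratory subgroup that is marked for figures in the study report, plus three overlapping criterion-9 comparisons. The primary result does not change. This should be corrected, but it does not threaten the trial's main conclusion.

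**What to change.** For the baseline-MMSE subgroup only, evaluate each band at its own mean baseline. This needs a separate LSMEANS statement with `at base=` for each band, keeping only that band's rows, because one AT value applies to all levels in a statement. Dropping the covariate for this subgroup, or fitting the bands separately, would also serve. State the choice in SAP 2.5.2, and say whether 10-14, 15-19 and 20-23 form one factor or a nested split.

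For the three overlapping comparisons, define disjoint groups, with the sponsor confirming the comparison intended, or run separate yes/no models. For 9-1 against 9-2, rely on the split into 9-1 only, 9-2 only and both that is already listed.

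The cost is a few lines of SAS and of SAP text, with no new data. The one loss is that the band estimates are no longer adjusted to a common baseline.
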